9.3.2 Pharmacokinetic Statistical Methodology

Two one-sided equivalence tests will be applied to the ratios of each of C_{max} and $AUC(0-\infty)$ using the AI as the test sample and the PFS as the reference. Test limits of the ratios to establish comparability are 0.8 and 1.25.

PK parameters will be evaluated to estimate the relative bioavailability. Log-transformed C_{max} and $AUC(0-\infty)$ will be evaluated in a linear mixed-effects model³ with fixed effects for device, sequence, period, and a random effect for subject within sequence. The treatment differences will be back-transformed to present the ratios of geometric means between AI and PFS treatments and the corresponding 90% CI. Other parameters may be analyzed in this way as needed.

Example SAS code for analysis:

```
proc mixed data=xxx;
    class sequence subject period device;
    model log_pk = sequence period device / ddfm=kr;
    random subject(sequence);
    lsmeans device / pdiff cl alpha=0.1;
    ods output lsmeans=lsmeans diffs=diffs;
run;
```

The t_{max} will be analyzed through non-parametric methods. The median for each treatment and median of differences between the AI and PFS treatments will be presented, along with the approximate 90% CI for the difference. The p-value from a Wilcoxon signed-rank test will also be presented.

9.4 Safety and Tolerability Assessments

9.4.1 Adverse events

Where changes in severity are recorded in the Case Report Form (CRF), each separate severity of the adverse event (AE) will be reported in the listings, only the most severe will be used in the summary tables. A pre-existing condition is defined as an AE that starts before the subject has provided written informed consent and is ongoing at consent. A non-treatment emergent AE is defined as an AE which starts after informed consent but prior to dosing. A treatment-emergent AE is defined as an AE which occurs postdose or which is present prior to dosing and becomes more severe postdose.

All AEs will be listed. Treatment-emergent AEs will be summarized by treatment (AI, PFS, and Overall), severity and relationship to the study drug. The frequency (the number of AEs, the number of subjects experiencing an AE and the percentage of subjects experiencing an AE) of treatment-emergent AEs will be summarized by treatment, Medical Dictionary for Regulatory Activities (MedDRA) version 22.0 system organ class and preferred term. The summary and frequency AE tables will be presented for all causalities and those considered related to the study drug by the investigator. Any serious AEs will be listed.

Discontinuations due to AEs will be listed.

Final: 08 August 2019 Page 12 of 16

9.4.2 Glucose Monitoring and Hypoglycemia

During the study, blood glucose concentrations will be monitored for safety assessments. Glucose data will be listed and summarized by treatment together with changes from baseline, where baseline is defined as Day 1 predose.

Hypoglycemic events will be appropriately recorded in the CRF. In the case of a hypoglycemic event, the actual blood glucose value, if measured, will be recorded in the CRF, together with any treatments administered. Each category of hypoglycemic events (defined below) will be listed and summarized by treatment. Hypoglycemia is defined as follows:

- Documented Glucose Alert Level (Level 1), Plasma Glucose (PG) ≤70 mg/dL (3.9 mmol/L):
 - o **Symptomatic hypoglycemia:** an event during which typical symptoms of hypoglycemia are accompanied by PG ≤70 mg/dL (3.9 mmol/L)
 - o **Asymptomatic hypoglycemia**: an event not accompanied by typical symptoms of hypoglycemia but with $PG \le 70 \text{ mg/dL}$ (3.9 mmol/L)
 - o **Unspecified hypoglycemia:** an event during which PG ≤70 mg/dL (3.9 mmol/L) but no information relative to symptoms of hypoglycaemia
- Documented Clinically Significant Hypoglycemia (Level 2) PG ≤54 mg/dL (3.0 mmol/L):
 - o **Symptomatic hypoglycemia:** an event during which typical symptoms of hypoglycemia are accompanied by PG ≤54 mg/dL (3.0 mmol/L)
 - o **Asymptomatic hypoglycemia:** an event not accompanied by typical symptoms of hypoglycemia but with PG \leq 54 mg/dL (3.0 mmol/L)
 - o **Unspecified hypoglycemia:** an event during which PG ≤54 mg/dL (3.0 mmol/L) but no information relative to symptoms of hypoglycemia was recorded
- Severe hypoglycemia (Level 3): an event requiring the assistance of another person to actively administer carbohydrate, glucagon, or other resuscitative actions. During these episodes, the subject has an altered mental status and cannot assist in their care, is semiconscious or unconscious, or experienced coma with or without seizures and may require parenteral therapy. Plasma glucose measurements may not be available during such an event, but neurological recovery attributable to the restoration of blood glucose concentration to normal is considered sufficient evidence that the event was induced by a low PG concentration (≤70 mg/dL [3.9 mmol/L]).
 - Severe hypoglycemia requiring medical attention: a severe hypoglycemic event when subjects require therapy by health care providers (emergency medical technicians, emergency room personnel, etc.).

Other Hypoglycemia:

• **Nocturnal hypoglycemia:** any hypoglycemic event (documented symptomatic, asymptomatic, probable symptomatic, or severe hypoglycemia) that occurs between bedtime and waking

Final: 08 August 2019 Page 13 of 16

- **Relative hypoglycemia:** an event during which typical symptoms of hypoglycemia, which do not require the assistance of another person, are accompanied by PG>70 mg/dL (3.9 mmol/L), but these levels may be quickly approaching the 70 mg/dL (3.9 mmol/L) threshold
- Overall (or total) hypoglycemia: this optional category combines all cases of hypoglycemia. If an event of hypoglycemia falls into multiple subcategories, the event is counted only once in this category
- **Probable symptomatic hypoglycemia:** an event during which symptoms of hypoglycemia are not accompanied by a PG measurement but that was presumably caused by PG ≤70 mg/dL (3.9 mmol/L).

Investigator review of glucose results clinically indicative of hypoglycemia will be required.

9.4.3 Concomitant medication

Concomitant medication will be coded using the WHO drug dictionary (Version March 2019). Concomitant medication will be listed.

9.4.4 Clinical laboratory parameters

All clinical chemistry and hematology data will be summarized by parameter and treatment, and listed. Urinalysis data will be listed. Additionally, clinical chemistry, hematology and urinalysis data outside the reference ranges will be listed and flagged on individual subject data listings.

9.4.5 Vital signs

Vital signs data will be summarized by treatment together with changes from baseline, where baseline is defined as the Day 1 predose assessment. Figures of mean vital signs and mean changes from baseline profiles will be presented by treatment.

Values for individual subjects will be listed.

9.4.6 Electrocardiogram (ECG)

ECGs will be performed for safety monitoring purposes only and will not be presented. Any clinically significant findings from ECGs will be reported as an AE.

9.4.7 Injection-Site Reactions

Injection-site assessments for local tolerability will be conducted, when reported as:

- an AE from a subject, or
- a clinical observation from an investigator.

Injection site assessment data (erythema, induration, categorical pain, pruritus, and edema) will be listed and summarized by treatment in frequency tables.

Final: 08 August 2019 Page 14 of 16

9.4.8 Hepatic Monitoring

If a subject experiences elevated alanine aminotransferase (ALT) $\ge 3 \times$ upper limit of normal (ULN), alkaline phosphatase (ALP) $\ge 2 \times$ ULN, or elevated total bilirubin (TBL) $\ge 2 \times$ ULN, liver tests will be performed to confirm the abnormality. Additional safety data may be collected if required, as defined in the protocol. Where applicable, the following will be presented.

The subjects' liver disease history and associated person liver disease history data will be listed. Any concomitant that have potential for hepatotoxicity, including acetaminophen will be listed. Results from any hepatic monitoring procedures, such as a magnetic resonance elastography (MRE) scan, and biopsy assessments will be listed, if performed.

Hepatic risk factor assessment data will be listed. Liver related signs and symptoms data will be summarized by treatment and listed. Alcohol and recreational drug use data will also be listed.

All hepatic chemistry, hematology, coagulation, and serology data will be listed. Values outside the reference ranges will be flagged on the individual subject data listings.

9.4.9 Hypersensitivity reactions

For all drug hypersensitivity reactions that occur, additional follow-up data will be collected to assess the patient's medical history, alternative causes, and symptoms.

These data will be listed.

9.4.10 Immunogenicity Assessments

Immunogenicity data will be listed and frequency tables will be presented. The frequency and percentage of patients with pre-existing antidrug antibody (ADA) and with treatment-emergent ADAs (TE ADAs) will be presented.

Treatment-emergent ADAs are defined as those with a titer 2-fold (1 dilution) greater than the minimum required dilution if no ADAs were detected at baseline (treatment-induced ADA) or those with a 4-fold (2 dilutions) increase in titer compared to baseline if ADAs were detected at baseline (treatment-boosted ADA). The minimum required dilution of the ADA assay is 1:10. For the TE ADA subjects, the distribution of maximum titers will be described. The frequency of neutralizing antibodies if performed, will be tabulated in TE ADA subjects. If cross-reactivity with to native GLP-1 and GIP or neutralizing antibodies against native GLP-1 and GIP assays are performed, the frequency of each will be reported.

9.4.11 Other assessments

All other safety assessments not detailed in this section will be listed but not summarized or statistically analyzed.

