• Follow-up: Period 2, Day 36 (±1) will be considered as the final follow-up visit

Number of Subjects:

Up to 48 subjects may be enrolled to ensure that approximately 36 subjects with evaluable results complete the study.

Statistical Analysis:

The primary PK parameters for analysis will be C_{max} and AUC(0-∞).

Two one-sided equivalence tests (TOST) will be applied to the ratios of each of C_{max} and AUC using the AI as the test sample and the PFS as the reference. Test limits of the ratios to establish comparability are 0.8 and 1.25.

Pharmacokinetic parameters will be evaluated to estimate the relative bioavailability. Log-transformed C_{max} and AUC(0- ∞) will be evaluated in a linear mixed-effects model with fixed effects for device, sequence, period, and a random effect for subject. The treatment differences will be back-transformed to present the ratios of geometric means and the corresponding 90% CI.

The t_{max} will be analyzed using a Wilcoxon signed rank test. Estimates of the median difference based on the observed medians and 90% CIs from the Wilcoxon test will be calculated.

Planned PK parameters will also be summarized with descriptive statistics.

All investigational product and protocol procedure AEs, and device complaints will be listed, and if the frequency of events allows, data will be summarized using descriptive methodology.

Safety parameters that will be assessed include adverse events, safety lab parameters (including amylase, lipase, and blood glucose), and vital signs. The parameters will be listed and summarized using standard descriptive statistics, where appropriate.

Physical examinations and ECGs will be performed for safety monitoring purposes and will not be presented. If warranted, additional analysis will be performed upon review of the data.

Incidence of erythema, induration, pain, itching, and edema will be listed and summarized.

Additional analyses may be performed, if appropriate.

2. Schedule of Activities

Study Schedule Protocol I8F-MC-GPGS

	Screening	Pe	eriods 1 an	nd 2 St	tudy E	Days –	at lea	st 35 d	lays wa	shout b	etween	Day 1	doses	EDc	Comments
Procedure	D-28 to D- 2	D-1b	D1b	D2	D3	D4	D5	D6	D7	D8	D15	D21	D36 (±1) ^b		
Informed Consent	Х														
Subject Admission to CRU		Х													
Tirzepatide Dosing			0 hour												Study drug will be administered after an overnight fast of at least 8 hours.

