9.2.2. Complaint Handling

Lilly collects product complaints on IPs and drug delivery systems used in clinical trials in order to ensure the safety of study participants, monitor quality, and to facilitate process and product improvements.

Subjects should be instructed to contact the investigator as soon as possible if he or she has a complaint or problem with the IP or drug delivery system so that the situation can be assessed.

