10.3.1. Safety Analyses

10.3.1.1. Clinical Evaluation of Safety

All IP, study device, and protocol procedure AEs, and study device deficiencies/complaints will be listed, and if the frequency of events allows, data will be summarized using descriptive methodology.

The incidence of symptoms for each treatment will be presented by severity and by association with IP as perceived by the investigator. Symptoms reported to occur prior to enrollment will be

distinguished from those reported as new or increased in severity during the study. Each symptom will be classified by the most suitable term from the medical regulatory dictionary.

The number of IP-related SAEs will be reported.

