Appendix 1. Abbreviations and Definitions

Term	Definition
AE	adverse event: Any untoward medical occurrence in a subject or clinical investigation subject administered a pharmaceutical product that does not necessarily have a causal relationship with this treatment. An AE can therefore be any unfavorable and unintended sign (including an abnormal laboratory finding), symptom, or disease temporally associated with the use of a medicinal (investigational) product, whether or not related to the medicinal (investigational) product.
assent	Agreement from a child or other individual who is not legally capable of providing consent, but who can understand the circumstances and potential risks involved in participating in a study (required by some ethical review boards [ERBs]).
CIOMS	Council for International Organizations of Medical Sciences
complaint	A complaint is any written, electronic, or oral communication that alleges deficiencies related to the identity, quality, purity, durability, reliability, safety or effectiveness, or performance of a drug or drug delivery system.
compliance	Adherence to all the study-related requirements, good clinical practice (GCP) requirements, and the applicable regulatory requirements.
confirmation	A process used to confirm that laboratory test results meet the quality requirements defined by the laboratory generating the data and that Lilly is confident that results are accurate. Confirmation will either occur immediately after initial testing or will require that samples be held to be retested at some defined time point, depending on the steps required to obtain confirmed results.
СР	Clinical Pharmacologist
CRP	Clinical Research Physician: Individual responsible for the medical conduct of the study. Responsibilities of the CRP may be performed by a physician, clinical research scientist, global safety physician or other medical officer.
enroll	The act of assigning a subject to a treatment sequence. Subjects who are enrolled in the study are those who have been assigned to a treatment sequence.
enter	Subjects entered into a study are those who sign the informed consent form directly or through their legally acceptable representatives.
ERB	ethical review board
GCP	good clinical practice
IB	Investigator's Brochure
ICF	informed consent form
ICH	International Council for Harmonization
IND	Investigational New Drug: An application to the FDA to allow testing of a new drug in humans.

I8F-MC-GPGS Clinical Pharmacology Protocol

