- For any questionable datum that does not satisfy the above criteria, the profile will be evaluated and results reported with and without the suspected datum.

Data between Individual Profiles

- 1. If n<6, then the dataset is too small to conduct a reliable range test. Data will be analyzed with and without the atypical value, and both sets of results will be reported.
- 2. If n≥6, then an objective outlier test will be used to compare the atypical value to other values included in that calculation:
 - a. Transform all values in the calculation to the logarithmic domain.
 - b. Find the most extreme value from the arithmetic mean of the log transformed values and exclude that value from the dataset.
 - c. Calculate the lower and upper bounds of the range defined by the arithmetic mean $\pm 3*SD$ of the remaining log-transformed values.
 - d. If the extreme value is within the range of arithmetic mean $\pm 3*SD$, then it is not an outlier and will be retained in the dataset.
 - e. If the extreme value is outside the range of arithmetic mean $\pm 3*SD$, then it is an outlier and will be excluded from analysis.

If the remaining dataset contains another atypical datum suspected to be an outlier and $n \ge 6$ following the exclusion, then repeat step 2 above. This evaluation may be repeated as many times as necessary, excluding only one suspected outlier in each iteration, until all data remaining in the dataset fall within the range of arithmetic mean $\pm 3*SD$ of the log-transformed values.

Reporting of Excluded Values

Individual values excluded as outliers will be documented in the final report. Approval of the final report will connote approval of the exclusion.

Final: 08 August 2019 Page 11 of 16

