11. CHANGES FROM THE PROTOCOL SPECIFIED STATISTICAL ANALYSES

There were no changes from the protocol specified statistical analyses.

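### Does the SAP's silence on device deficiencies and complaints, which the protocol plans to list and conditionally summarize, call for a change?

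*SAP*

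**What the plan says.** Protocol 10.3.1.1 states that "study device deficiencies/complaints will be listed, and if the frequency of events allows, data will be summarized using descriptive methodology". The statistical part of the protocol synopsis matches it: "All investigational product and protocol procedure AEs, and device complaints will be listed, and if the frequency of events allows, data will be summarized". Protocol 9.2.2 confirms that the information is gathered: "Lilly collects product complaints on IPs and drug delivery systems used in clinical trials". Appendix 1 of the protocol defines a complaint broadly, as any communication that "alleges deficiencies related to the identity, quality, purity, durability, reliability, safety or effectiveness, or performance of a drug or drug delivery system".

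The SAP mentions neither complaints nor deficiencies. Section 9.4 gives adverse events, glucose, laboratory data, vital signs, injection-site reactions and other topics their own subsections, but not device complaints. Two general rules then apply:

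- Section 9.1 promises listings of everything in the database and confines summaries to data that the SAP details.
- Section 9.4.11 adds: "All other safety assessments not detailed in this section will be listed but not summarized or statistically analyzed".

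Section 3 says that the SAP takes precedence over the protocol's statistical section and that substantial differences will be identified. Section 11 states: "There were no changes from the protocol specified statistical analyses".

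**The concern.** The study exists to compare two delivery devices, and the autoinjector is the intended commercial product. A complaint need not involve an adverse event. An injection that stalls or leaks without causing symptoms would appear in no adverse event table and no injection-site table. If the SAP drops the complaint output, the device record most specific to this trial could disappear from the report.

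There is also a possible link to the primary endpoint. A delivery fault could produce a low Cmax or AUC. Under the between-profile outlier steps in SAP 9.3.1, a value more than 3 SD from the mean of the remaining log-transformed values is handled as follows: "then it is an outlier and will be excluded from analysis". Those steps do not refer to any delivery record. A reader without the complaint record could not tell a device failure from an unusual subject. Finally, Section 11 says that nothing changed, although one planned output has no counterpart in the SAP.

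**Working it through.** The plan gives no figure on this point, so the check is mainly a comparison of texts.

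**1. What each document yields**

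| Output | Protocol 10.3.1.1 and synopsis | SAP as written |
|---|---|---|
| Listing of deficiencies/complaints | Yes | Yes under 9.4.11 if they count as an other safety assessment; otherwise yes under 9.1 if they are databased |
| Descriptive summary | Only if frequency allows | No (9.1 and, where it applies, 9.4.11) |
| AEs related to device or procedure | Listed; summarized if frequency allows | All AEs listed; all-causality tables by device; no separate device-related split |

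The protocol places complaints under its clinical evaluation of safety, so reading them as a safety assessment is natural. Section 9.4.11 then bars the summary and grants the listing in the same sentence. The listing would be lost only if complaints were outside 9.4.11 and also not databased. Protocol 9.2.2 does not say whether they enter the clinical database, so a transfer may be needed, but nothing says that they do not.

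**2. How much the missing summary could hold**

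Each subject receives two injections:

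- 36 completers: 36 × 2 = 72 injections, 36 per device.
- 48 subjects: 48 × 2 = 96 injections at most, 48 per device.

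The documents give no complaint rate. A complaint summary would be a count by device over 36 to 48 injections, which a reader can obtain from a listing that identifies subject and treatment. If complaints are few, the protocol's own condition is not met and the two plans produce the same output.

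**3. Adverse events**

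SAP 9.4.1 states: "Treatment-emergent AEs will be summarized by treatment (AI, PFS, and Overall), severity and relationship to the study drug". The same section presents its tables for all causalities as well as for events related to study drug. An event that the investigator attributes to a device or a procedure is therefore counted under the device used. Protocol 10.3.1.1 itself plans the incidence display by severity and by association with the investigational product, and SAP 9.4.1 follows that.

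**4. Excluded PK values**

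SAP 9.3.1 describes the outlier procedure as optional, does not allow it to remove complete profiles, and requires excluded values to be documented in the final report. With those values documented and complaints listed, a reader can match the two.

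**5. Section 11**

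Section 3 asks only for substantial differences to be identified. It also says that analyses generally follow the protocol unless modified by agreement, and it permits supplementary analyses that are identified in the study report. One conditional descriptive table is at most a marginal case for that duty.

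**The case for a change.** The strongest case starts from the fact that the texts do differ and that the SAP takes precedence, so the protocol sentence cannot simply be read into it. In a device comparison the complaint record matters more than in an ordinary PK study, and under-delivery would act directly on the primary ratio. Suppose, purely as an assumption, that one autoinjector injection among 36 delivers half the dose and that exposure is proportional to dose. The geometric mean ratio is then multiplied by 0.5^(1/36) = 0.981. Three such injections give 0.5^(3/36) = 0.944.

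The difference between the texts stands. The consequence does not. Applied to the planning ratio of 1.05, the multipliers give 1.05 × 0.981 = 1.030 and 1.05 × 0.944 = 0.991. Both are nearer to 1 and well inside 0.80 to 1.25. More to the point, these figures describe an assumed fault. They are the same whether complaints are tabulated, only listed, or noted in Section 11, so they do not measure the gap. Whether the outlier rule would remove such a value is likewise a question about that rule, and a complaint table would not alter the answer.

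It is also fair to say that a listing is less convenient than a table, and that the SAP does not name the source of the complaint data. Both are matters of presentation and data handling, which the study team can settle when it builds the outputs.

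**Conclusion.** No change to the plan follows. The mismatch is genuine: the SAP omits a frequency-conditional descriptive summary that the protocol announces, and Section 11 does not record the omission. Its size is at most one count table by device over 72 to 96 planned injections, and possibly nothing if complaints are rare. If the SAP is followed exactly, the two one-sided tests on Cmax and AUC(0-∞), the adverse event incidence by device and the study's conclusion are the same as they would be with the table.

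This rests on two readings. First, complaints are treated as a safety assessment, as the protocol does, or are databased; either is enough to keep the listing. Second, if complaints turn out to be frequent, analysts use the latitude in SAP Section 3 to tabulate them and say so in the report. The TFL shells named in that section were not available and may already provide for this. The conclusion concerns the SAP text alone.
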